3.2 Biomarker Variables

PD-L1 expression status (high, low) will be defined for the analysis of Module A according to following criteria:

- High: \geq 25% tumour cell or immune cell membrane positivity for PD-L1 at any intensity above background staining as noted on the corresponding negative control.
- Low: < 25% tumour cell and immune cell membrane positivity for PD-L1 at any intensity above background staining as noted on the corresponding negative control.

3.3 Efficacy

3.3.1 Secondary endpoint

3.3.1.1 Overall survival (OS)

OS is defined as the time from the date of first dose until death due to any cause (ie, date of death or censoring – treatment start date + 1). Any patient not known to have died at the time of analysis will be censored based on the last recorded date on which the patient was known to be alive (SUR_DAT, recorded within the SURVIVE module of the electronic case report form [eCRF]).

Note: Survival calls will be made in the week following the date of Data Cut Off (DCO) for the analysis, and if patients are confirmed to be alive or if the death date is post the DCO date these patients will be censored at the date of DCO. The status of ongoing, withdrawn (from the study) and "lost to follow-up" patients at the time of the final OS analysis should be obtained by the site personnel by checking the patient's notes, hospital records, contacting the patient's general practitioner and checking publicly-available death registries. In the event that the patient has actively withdrawn consent to the processing of their personal data, the vital

status of the patient can be obtained by site personnel from publicly-available resources where it is possible to do so under applicable local laws.

Note that for any OS analysis performed prior to the final OS analysis, in the absence of survival calls being made, it may be necessary to use all relevant CRF fields to determine the last recorded date on which the patient was known to be alive for those patients still on treatment (since the SURVIVE module is only completed for patients off treatment).

3.3.2 Exploratory endpoints

RECIST 1.1 response will be assessed by the investigator and not derived programmatically since tumor evaluation will be carried out by the sites per institution standards and detailed tumor measurements are not databased.

3.3.2.1 Objective response

Objective response (using Investigator assessments) is defined as at least 1 visit response of CR or PR. Data obtained up until progression, or the last evaluable assessment in the absence of progression, will be included in the assessment of objective response. Patients who go off treatment without progression, receive a subsequent therapy, and then respond will not be considered responders.

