1.4 Study Design

This is an open-label, multi-center, study to determine safety of fixed doses of durvalumab 1500 mg and tremelimumab 75 mg combination therapy or durvalumab 1500 mg monotherapy in patients with advanced solid malignancies.

The protocol (and each tumor specific module in APPENDIX F) consists of a screening period, a treatment period, a safety follow up period (90 days post treatment discontinuation), and a survival follow up period.

Patients will attend a safety follow up visit 90 days after study treatment discontinuation. Thereafter, patients will be contacted by phone or electronic communication every 3 months for survival status until the final data cut-off (DCO).

Investigational product, dosage and mode of administration

Durvalumab + tremelimumab combination therapy

- Durvalumab 1,500 mg plus tremelimumab 75 mg via IV infusion once every 4 weeks (Q4W), starting on Week 0, for up to a maximum of 4 doses (or cycles) followed by:
- Durvalumab monotherapy 1,500 mg via IV infusion Q4W, starting 4 weeks after the last infusion of the combination or discontinuation of tremelimumab.

OR

Durvalumab monotherapy

• Durvalumab 1,500 mg via IV infusion Q4W, starting on Week 0.

Each tumor specific module (APPENDIX F) will specify combination therapy or monotherapy, and will provide details of infusion duration.

Duration of treatment

Patients may continue receiving therapy as long as they are continuing to demonstrate clinical benefit, as judged by the Investigator, and in the absence of initiation of alternative cancer treatment, unacceptable toxicity, withdrawal of consent, or other reason for treatment discontinuation.

Unless specific treatment discontinuation criteria are met patients will continue therapy until disease progression.

Progression during treatment

During the treatment period, patients may continue receiving therapy in the setting of unconfirmed progressive disease (PD) according to Response Evaluation Criteria in Solid Tumors version 1.1 (RECIST 1.1), at the Investigator's discretion, until progression is confirmed^{*}. A confirmatory scan is required following a RECIST 1.1 overall time point assessment of progression (PD), preferably at the next scheduled visit and no earlier than 4 weeks after the previous assessment of PD.

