Patients with PD by RECIST 1.1 (unconfirmed and confirmed) who, in the Investigator's opinion, continue to receive benefit from their treatment and who meet the criteria for treatment in the setting of PD may continue to receive treatment for as long as they are gaining clinical benefit.

However, patients will not be permitted to continue immunotherapy if progression occurs after confirmed response (complete response [CR] or partial response [PR] as defined by RECIST 1.1) to immunotherapy treatment in target lesions (regardless of the appearance of new lesions), ie, the response and progression events both occurred in the target lesions while receiving immunotherapy during the same treatment period.

Patients in Modules with combination durvalumab + tremelimumab may restart treatment with the combination if they complete the 4 dosing cycles with durvalumab + tremelimumab (with clinical benefit per Investigator judgement) but subsequently have PD during treatment with durvalumab alone and provided they meet eligibility criteria for retreatment.

See Section 7.8 for post-study access to treatment information.

[figure not shown]
^{*} Where treatment is discontinued due to progressive disease, it is recommended that a confirmatory scan be performed prior to discontinuation to verify progression. According to RECIST 1.1 modified for confirmation of progression, a confirmatory scan is required following an overall time point assessment of progression (PD), no earlier than 4 weeks after the previous assessment of PD.

Follow up of patients post discontinuation of study drug

Patients who have discontinued treatment due to toxicity or symptomatic deterioration, clinical progression, or withdrawal from treatment, or patients who have started a subsequent anticancer therapy, will have one additional tumor assessment on a subsequent scan, if clinically feasible, will be followed up for AEs for 90 days, and thereafter followed up for survival (described in the next section). These patients are not eligible for re-treatment at any time.

Follow Up for Safety and Survival

Patients will attend a safety follow up visit 90 days after study treatment discontinuation. Thereafter, patients will be contacted by phone or email every 3 months for survival status until the final DCO.

Tumor specific modules (APPENDIX F) detail which treatment regimen, combination therapy or monotherapy, will be used.

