Patients may continue receiving therapy in the setting of unconfirmed progressive disease (PD), at the Investigator's discretion, until PD is confirmed*. Patients with PD by RECIST 1.1 (unconfirmed and confirmed) who, in the Investigator's opinion, continue to receive benefit from their assigned treatment and who meet the criteria for treatment in the setting of PD may continue to receive treatment for as long as they are gaining clinical benefit.

However, patients will not be permitted to continue immunotherapy if progression occurs after confirmed response (CR or PR as defined by RECIST 1.1) to immunotherapy treatment in target lesions (regardless of the appearance of new lesions) i.e., the response and progression events both occurred in the target lesions while receiving immunotherapy during the same treatment period.

Patients in Modules with combination durvalumab + tremelimumab may restart treatment with the combination if they complete the 4 dosing cycles with durvalumab + tremelimumab (with clinical benefit per Investigator judgement) but subsequently have PD during treatment with durvalumab alone and provided they meet eligibility criteria for re-treatment.

[figure not shown]
*Where treatment is discontinued due to progressive disease, it is recommended that a confirmatory scan be performed prior to discontinuation to verify progression. According to Response Evaluation Criteria in Solid Tumors version 1.1 (RECIST 1.1) modified for confirmation of progression, a confirmatory scan is required following an overall time point assessment of PD, no earlier than 4 weeks after the previous assessment of PD.

Follow up of patients post discontinuation of study drug

Patients who have discontinued treatment due to toxicity or symptomatic deterioration, clinical progression, or who have commenced subsequent anticancer therapy, will be followed up until confirmed disease progression and for survival.

Follow up for safety and survival

Patients will attend a safety follow-up visit 90 days after study treatment discontinuation. Thereafter, patients will be contacted by phone or email every 3 months for survival status until the final DCO

Tumor specific modules detail which treatment regimen, combination therapy or monotherapy, will be used.

Patients will continue to receive study treatment as long as they are receiving clinical benefit in the opinion of the Investigator unless any of the criteria for treatment discontinuation are met first.

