3.3.2.2 Disease control rate

Disease control at 6 or 12 months is defined as a best objective response (BoR) of CR or PR or stable disease (SD) as assessed by the investigator, in the first 6 or 12 months, respectively, following the start of study treatment.

Disease control will be determined based on the Investigator assessments and all data up until the first confirmed progression event. This will use all data up until the progression event that is used for the analysis (ie, unconfirmed progressions are not considered progression events, which means that the BoR that contributes to the assessment of disease control may be after an unconfirmed progression for some patients). Patients who go off treatment without progression, receive a subsequent therapy, and then respond will not be considered responders.

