4. ANALYSIS METHODS

4.1 General principles

No hypothesis testing is planned for this single arm study. Each module will be summarised separately.

The general principles as mentioned below will be followed throughout the study:

- Descriptive statistics will be used for all variables, as appropriate, and will be presented separately for each module. Descriptive safety and efficacy data from the STRONG study may be utilized as supporting evidence for health authority considerations.
- Continuous variables will be summarized by the number of observations, mean, standard
 deviation, median, minimum, and maximum. For log transformed data it is more
 appropriate to present geometric mean, coefficient of variation (CV), median, minimum
 and maximum. Categorical variables will be summarized by frequency counts and
 percentages for each category.
- Unless otherwise stated, percentages will be calculated out of the population total.
- Exact CIs for proportions will be calculated using the Clopper-Pearson method.
- For percentiles of survival times based on the Kaplan-Meier method (eg, median survival), CIs will be calculated using the default method available in the SAS LIFETEST procedure (ie, the Klein and Moeschberger extension of the Brookmeyer-Crowley method).
- For point-estimates of survival based on the Kaplan-Meier method (eg, for OS at 12 months), CIs will be calculated using the default method available in the SAS LIFETEST procedure (ie, using Greenwood's estimate of standard error and a log-log transformation).
- For continuous data the mean and median will be rounded to 1 additional decimal place compared to the original data. The standard deviation will be rounded to 2 additional decimal places compared to the original data. Minimum and maximum will be displayed with the same accuracy as the original data.
- For categorical data, percentages will be rounded to 1 decimal place.
- SAS® version 9.3 or higher will be used for all analyses.

Baseline will be the last assessment of the variable under consideration prior to the intake of the first dose of study treatment.

All data collected will be listed.

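### The planned ORR is an unconfirmed response rate: label it so, show a confirmed rate beside it, and say which progression closes its window

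*SAP*

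**What the plan says.** SAP section 3.3.2.1 defines the endpoint: "Objective response (using Investigator assessments) is defined as at least 1 visit response of CR or PR". The data window follows: "Data obtained up until progression, or the last evaluable assessment in the absence of progression, will be included in the assessment of objective response". That sentence does not say whether the progression must be confirmed. Responses that appear only after a subsequent therapy are excluded.

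SAP section 3.3.2.2, on disease control rate (DCR), is explicit on the same question: "Disease control will be determined based on the Investigator assessments and all data up until the first confirmed progression event". It adds that "unconfirmed progressions are not considered progression events", and accepts that the best response used may come after an unconfirmed progression.

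Protocol section 1.4 asks for a second look at progression: "A confirmatory scan is required following a RECIST 1.1 overall time point assessment of progression (PD), preferably at the next scheduled visit". Neither document has a counterpart for CR or PR. The idea of a confirmed response does appear, but in the rule on continuing treatment (SAP section 1.2): "However, patients will not be permitted to continue immunotherapy if progression occurs after confirmed response".

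SAP section 3.3.2 says that response is the investigator's call, that tumours are evaluated by each institution's standard, and that measurements are not held in the database. ORR and DCR are exploratory (SAP section 1.1.3), nothing is tested, and SAP section 4.2.2 reports both with exact 95% intervals. On use of the results, SAP section 4.1 says: "Descriptive safety and efficacy data from the STRONG study may be utilized as supporting evidence for health authority considerations".

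**The concern.** A response seen at one visit may be real and lasting, real and brief, or a misreading. Confirmation separates the first from the other two. Without it, each further assessment gives a non-responder another chance to be counted. Three usual safeguards are absent here: there is no control arm in which the same errors would occur, the assessor is the investigator, and responses cannot be re-derived from measurements.

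What is at stake is interpretation. A table row headed ORR with a 95% interval, also broken down by the nine subgroup factors in SAP section 4.2.1, does not tell the reader that it is an unconfirmed rate. Someone who sets it beside a confirmed rate from elsewhere compares two different quantities, and nothing planned would show how far apart they are. The possible use before health authorities makes this more than a matter of wording.

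**Working it through.** **Inputs from the documents.** Responder rule: one visit of CR or PR (SAP 3.3.2.1). Sample size for Module A: 600 to 1200 (SAP 1.3). Interval method: Clopper-Pearson (SAP 4.1, 4.2.2). The documents give no expected ORR and no share of responses that would be confirmed.

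**Inputs assumed.** Single-visit ORR of 10%, 15% or 20%; confirmed share c between 70% and 100%; all patients in the denominator. (SAP 4.2.2 uses patients with an assessment; a smaller common denominator scales both rates alike.)

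**1. Check of the interval method.** The plan states no ORR figure, but SAP Table 1 gives exact intervals for general incidences. Recomputed at n = 1200: 10% gives 8.36 to 11.84, 15% gives 13.03 to 17.15, 20% gives 17.77 to 22.38. The table prints 8.4-11.8, 13.0-17.2 and 17.8-22.4, so the method reproduces.

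**2. Direction.** Every patient with two qualifying assessments has at least one. Confirmed responders are therefore a subset of single-visit responders, and on a common denominator confirmed ORR ≤ single-visit ORR, with equality if every response is confirmed.

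**3. Size.** Confirmed ORR = c × single-visit ORR, so the gap = (1 − c) × single-visit ORR. For a single-visit ORR of 15% at n = 1200 (180 responders):

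| c | Confirmed responders | Confirmed ORR | Exact 95% CI | Gap (points) |
|---|---|---|---|---|
| 100% | 180 | 15.0% | 13.0 to 17.1 | 0 |
| 95% | 171 | 14.25% | 12.3 to 16.4 | 0.75 |
| 90% | 162 | 13.5% | 11.6 to 15.6 | 1.5 |
| 80% | 144 | 12.0% | 10.2 to 14.0 | 3.0 |
| 70% | 126 | 10.5% | 8.8 to 12.4 | 4.5 |

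The largest gap, at c = 70%, is 0.30 × 10% = 3.0 points, 0.30 × 15% = 4.5 points, or 0.30 × 20% = 6.0 points. The smallest is zero in each case. The gap does not depend on n.

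**4. Mechanism, also on assumptions.** Take a true ORR of 15%, four assessments, and an independent chance f of a false CR or PR per visit in a non-responder. The single-visit rule gives 15% + 85% × [1 − (1 − f)^4]: 18.3% at f = 1% and 21.6% at f = 2%. Requiring two consecutive responses, with all true responders still counted, gives 15.0% and 15.1%. This shows how repeated looks can add responders; it does not estimate this trial's error rate.

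**5. The data window.** DCR stops at the first confirmed progression. ORR stops at progression, unqualified. If that means confirmed progression, a CR or PR after an unconfirmed progression counts towards ORR; if it means any progression, it does not. The SAP supports either reading, so two programmers could produce different responder counts.

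**The case against.** The strongest reply is that the SAP defines its endpoint openly, never calls it a confirmed rate, and plans no comparison with one. ORR is exploratory in a safety study, the efficacy endpoint at secondary level is overall survival, and there is no hypothesis test or decision rule. Confirmed response in the treatment-continuation rule is not an endpoint definition and does not contradict section 3.3.2.1. All of this stands, and it limits the point to labelling and a companion figure.

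A second reply concerns feasibility, and much of it stands too. No confirmatory response scan is scheduled. Protocol Table 2 leaves tumour assessment to institutional standard, while Protocol section 4.2.2 has the investigator's response assessment recorded before each dose. Two consecutive visits with PR may therefore rest on one scan, which confirms nothing. Conversely, a true responder with no second scan would be counted as unconfirmed, so the confirmed rate can err downwards. These are good reasons not to make confirmed ORR the main figure. They are not reasons to omit it, provided that patients who could not be confirmed are counted separately.

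A reader might also infer that the plan is lenient at both ends, with response unconfirmed and progression confirmed, and that this asymmetry raises ORR. The documents do not support that. The confirmed-progression rule is written for DCR, its consequence is stated there, and it fits a design that allows treatment through unconfirmed progression. It would touch ORR only if the unqualified word in section 3.3.2.1 were read as confirmed progression, which the SAP does not say.

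**Conclusion.** The ORR as defined is an unconfirmed rate, equal to or above a confirmed ORR. That follows from the single-visit rule alone and needs no assumption beyond a common denominator. The size does need assumptions: 0 to 6.0 points over an assumed ORR of 10% to 20% and an assumed confirmed share of 70% to 100%. No single corrected figure can be derived from the documents.

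Two stronger conclusions should be avoided. One is that the ORR is overstated: the gap may be zero, and the SAP does not claim to estimate a confirmed rate. The other would use the interval as proof of bias. In the table above, 12.0% lies below the lower limit of 13.0% for the single-visit rate. But that interval describes sampling error in a different quantity, so a confirmed rate falling outside it does not demonstrate bias.

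No error rate or primary conclusion is affected. What improves is what can be concluded from the ORR if it is used as section 4.1 allows.

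**What to change.** In SAP sections 3.3.2.1 and 4.2.2:

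- Keep the present measure and label it unconfirmed ORR in text, tables and subgroup displays.
- Beside it, with the same denominator and exact 95% interval, report a confirmed ORR: CR or PR at two separate tumour assessments at least 4 weeks apart, with no PD between them. Specify that two visit entries resting on the same scan do not qualify.
- Report the number of unconfirmed responders who had no second tumour assessment, so that not assessable is kept apart from not confirmed.
- State whether the progression that closes the ORR window is confirmed or unconfirmed.

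The cost is SAP wording and one extra derivation from visit responses already recorded, with no new assessments. The second figure will be equal or lower, and some responders will be unconfirmable because scans follow institutional schedules. Protocol section 4 allows visit windows of 3 to 5 days and dosing intervals down to 22 days, so a strict 4-week rule will also miss some assessments made on schedule; the count in the third item shows only those with no second assessment, so these should be footnoted. The documents do not say whether the database identifies the scan behind each visit response. Check this first, and if it does not, state that limit beside the confirmed figure.

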3.3.2.2 Disease control rate

Disease control at 6 or 12 months is defined as a best objective response (BoR) of CR or PR or stable disease (SD) as assessed by the investigator, in the first 6 or 12 months, respectively, following the start of study treatment.

Disease control will be determined based on the Investigator assessments and all data up until the first confirmed progression event. This will use all data up until the progression event that is used for the analysis (ie, unconfirmed progressions are not considered progression events, which means that the BoR that contributes to the assessment of disease control may be after an unconfirmed progression for some patients). Patients who go off treatment without progression, receive a subsequent therapy, and then respond will not be considered responders.

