4.2.2 Efficacy data

Overall survival

OS will be summarised using the Kaplan-Meier method with median OS and its associated 95% confidence interval reported as well as the proportion of patients alive at 1, 2, 3, 4 and 5 years.

Objective Response Rate and Disease Control Rate

Objective response rate (ORR) and Disease control rate (DCR) at 6 and 12 months will be calculated for the SAF as the percentage of patients (%) with objective response and

controlled disease, respectively. ORR and DCR will be reported with the associated 95% exact Clopper-Pearson confidence interval.

The denominator used for ORR and DCR rates will be the number of patients with an assessment in the time period. A summary of investigator assessment (responding, stable or progressing) will be provided for those patients with an alternative method of assessment (e.g. WHO).

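### DCR is labelled as disease control at 6 and 12 months but is derived as best response within those windows, with no minimum SD duration in the SAP or core protocol, so control lost before the landmark still counts.

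*SAP*

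**What the plan says.** SAP section 3.3.2.2 defines the endpoint: "Disease control at 6 or 12 months is defined as a best objective response (BoR) of CR or PR or stable disease (SD", as judged by the investigator, "in the first 6 or 12 months, respectively, following the start of study treatment". The derivation uses "all data up until the first confirmed progression event", and "unconfirmed progressions are not considered progression events".

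SAP section 4.2.2 carries the label forward without repeating the window: "Objective response rate (ORR) and Disease control rate (DCR) at 6 and 12 months will be calculated for the SAF". It sets the denominator: "The denominator used for ORR and DCR rates will be the number of patients with an assessment in the time period". It adds a Clopper-Pearson interval.

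SAP section 3.3.2 leaves scan timing to local practice: "tumor evaluation will be carried out by the sites per institution standards and detailed tumor measurements are not databased". Protocol section 4.2.2 lists the investigator's response assessment among the pre-dose steps at treatment visits, so a very early SD entry is possible.

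Protocol section 2.3 names DCR by investigator RECIST 1.1 as an exploratory objective and gives neither a time point nor an SD duration. The protocol synopsis and section 8 refer to the tumor-specific modules for statistical detail. Module A is not among the documents available here.

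**The concern.** The label and the derivation describe different quantities. A reader shown DCR at 12 months will take it as the share of patients whose disease was still controlled at one year. The derivation asks only whether a CR, PR or SD was ever recorded in the first year before confirmed progression. Confirmed progression stops later readings from being used but does not cancel an earlier SD. Death is not mentioned.

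Two consequences follow. A single early SD reading can qualify a patient for both time points. And the 12-month figure cannot register control lost between months 6 and 12, which is the information its name promises.

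DCR is exploratory, but it is one of the two measures in that objective and is repeated across nine subgroup factors (SAP section 4.2.1). SAP section 4.1 also allows the descriptive efficacy results to be put before health authorities in a supporting role.

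**Working it through.** The documents state no DCR figure, so there is nothing to reproduce. The check applies the rule to one patient, then to the two numerators, then to an assumed population.

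**1. One patient.** SD at week 8, confirmed progression at week 16, death at month 5. The usable data are those before week 16, and the best response in them is SD. Week 8 lies inside both windows. The patient is counted as controlled at 6 months and again at 12 months, seven months after death (12 − 5 = 7).

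The result depends on the week-8 entry:
- If the only assessment is confirmed progression, the patient is in the denominator and not controlled.
- If the patient dies before any assessment, the patient leaves the denominator under section 4.2.2.
- If the progression is never confirmed, it is not an event for DCR at all.

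**2. The two numerators.** The first 6 months are contained in the first 12, so everyone counted at 6 months is counted at 12. The numerator can stay level or rise but not fall. The two rates can differ only through patients whose first assessment, or first CR, PR or SD, falls between months 6 and 12.

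**3. Size, simple case.** All inputs are assumptions: exponential time to progression or death with median *m* months; first scan at 2 months; everyone unprogressed then rated SD or better; all treated patients in the denominator. The share without an event by month *t* is 2^(−t/m). The SAP rule equals this value at *t* = 2, for both reported times.

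| Median *m* | SAP rule, both times: 2^(−2/m) | Progression-free at month 6: 2^(−6/m) | Progression-free at month 12: 2^(−12/m) |
|---|---|---|---|
| 2 months | 50% | 12.5% | 1.6% |
| 3 months | 63% | 25% | 6.3% |
| 4 months | 71% | 35% | 12.5% |

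**4. Size, with scan timing and the SAP denominator varied.** Let the first scan fall at *s* months, let *q* = 2^(−s/m), and let a fraction *f* of events be deaths with no progression scan. Early unscanned deaths drop out of the denominator, so the SAP rate is q / (1 − f(1 − q)). Weeks convert to months as weeks × 12/52.1775, so 6, 8 and 12 weeks are 1.38, 1.84 and 2.76 months.

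- *m* = 4, 8 weeks, *f* = 0: q = 2^(−1.84/4) = 72.7%, the same at both times. Progression-free: 35% at month 6, 12.5% at month 12.
- Same, *f* = 0.3: 0.727 / (1 − 0.3 × 0.273) = 79.2%. The denominator alone adds 6.5 points.
- Lowest (*m* = 2, 12 weeks, *f* = 0): 2^(−2.76/2) = 38.4%.
- Highest (*m* = 6, 6 weeks, *f* = 0.3): q = 2^(−1.38/6) = 85.3%, and 0.853 / (1 − 0.3 × 0.147) = 89.2%.

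A simulation of 1,000,000 patients per scenario (*m* = 2, 3, 4, 6; scans every 6, 8 or 12 weeks; *f* = 0 or 0.3) agrees: 38% to 89% under the SAP rule, identical at 6 and 12 months in every scenario. The share progression-free was about 12.5% to 50% at month 6 and 1.6% to 25% at month 12. The 6- and 12-month values are identical because every assumed first scan falls before month 6. At *m* = 4, moving the scan interval from 12 to 6 weeks raises the SAP rate from 61.9% to 78.8% with no change in the disease.

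**The case against.** The strongest reply is that this is a labelling matter. Section 3.3.2.2 discloses the window in the same sentence, a programmer would derive one unambiguous variable, and the SAP nowhere claims that DCR measures durability. Disclosure in 3.3.2.2 is real, but 4.2.2 drops the window and keeps the landmark wording, and results will be read under that name.

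Three stronger readings are tempting, and the documents do not support them.

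- A reader might infer that anyone who progresses or dies at month 4 is counted as controlled. That holds only if a CR, PR or SD was recorded first.
- A reader might divide the columns in step 3 and say that DCR is overstated 2- to 4-fold at 6 months and about 6- to 32-fold at 12. Those ratios compare two different quantities and are an overstatement only if landmark status was intended, which the protocol objective does not establish. They also rest on one assumed scan time and on a denominator that differs from section 4.2.2.
- A reader might conclude that no minimum SD duration exists anywhere. Module A was not seen and may contain one. Even so, a minimum duration shorter than the landmark would not make the 12-month label true.

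Two further points stand. DCR is exploratory in a single-arm safety study with no hypothesis testing. And a landmark endpoint is harder to fill: scans follow local practice, and follow-up after discontinuation is described as one further tumor assessment where feasible (protocol section 1.4) or as continuing to confirmed progression (protocol section 7.2.1, SAP section 1.2). Any landmark rule therefore needs a missing-assessment rule. The OS proportions at 1 to 5 years are time-based, but they do not measure disease control.

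**Conclusion.** The point holds for the SAP and core protocol as supplied. The quantity reported as DCR at 6 and 12 months is best disease control reached within those windows. It retains patients who had a qualifying reading and then progressed or died before the landmark, and its 12-month count cannot fall below its 6-month count. Neither conclusion needs a numerical assumption.

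The size does. Under the assumptions of step 3 the rule gives 50% to 71% at both times, beside 12.5% to 35% progression-free at month 6 and 1.6% to 12.5% at month 12. Actual values depend on scan timing and on how many patients have no assessment. The primary safety outcome is untouched. The change should still be made before DCR is reported or used as supporting evidence.

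**What to change.** In SAP section 3.3.2.2, define disease control at 6 (12) months as either CR or PR in the first 6 (12) months, or SD maintained to month 6 (12) less a stated visit window, with no confirmed progression, death or subsequent anticancer therapy before then. State how patients with no assessment in that window are counted, for example as not controlled. Report separately those first dosed less than 6 (12) months before the DCO. If status at the landmark is wanted for every patient, require CR and PR patients to be unprogressed at month 6 (12) as well.

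If the best-response version is kept, call it best disease control within the first 6/12 months in both 3.3.2.2 and 4.2.2, state a minimum SD duration, and do not present it as control at 6 or 12 months.

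Cost: wording in two sections and, for the landmark version, re-derivation of one variable from the investigator's response dates plus the missing-assessment rule. The reported DCR will fall, and some off-treatment patients will lack a landmark assessment. Neither version removes the influence of locally chosen scan times.
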